4.2 Treatment Duration

Phase Ib subjects who developed a DLT with the first cycle will be taken off study at the Cycle 1 Day 28 visit.

For all others, treatment with ciprofloxacin and etoposide will be repeated in 28-day cycles until:

- In Cycle 2, if the treating physician decides that the subject has rapidly progressive disease despite treatment;
- Subject withdrawal of consent for continued participation in the study;
- Inter-current illness that prevents further administration of study treatment;
- Unacceptable toxicity attributed to study treatment with ciprofloxacin and etoposide;
- Completion of 2 cycles of therapy from Day 1, Cycle 1;
- Disease progression defined by >25% increase in marrow blasts ([Appendix A](#));
- If, in the opinion of the PI or treating physician, continuation in the study could be detrimental to the subject's well-being;
- Significant deviation from inclusion/exclusion criteria in the opinion of the PI;
- Lost to follow-up (discontinuation date will be recorded as the date of last contact with subject); and/or
- Termination of the study.

Subjects with an ANC < 500/ μ L at the Day 28 assessment will be treated unless the Day 28 bone marrow shows < 5% cellularity. In that event, treatment will be held and a CBC will be repeated weekly until Day 42. A bone marrow will be repeated no later than Day 42 for subjects who

have treatment held. In the event that the subject does not show bone marrow recovery with a cellularity > 5% by Day 42 of treatment, the subject will be withdrawn from the study.

Table 3. Dosing Modifications

Event	Action
Disease Progression	Stop Therapy
ANC > 500/ μ L, No progression	Resume Therapy
ANC < 500/ μ L, Cellularity > 5%, No progression	Resume Therapy

4.3 Supportive Care

Supportive care will be administered to all study subjects per institutional guidelines.

Subjects should be prescribed and counseled to take an anti-emetic 30 – 60 minutes prior to all etoposide doses. Subjects should be counseled to take etoposide capsules on an empty stomach.

Subjects should be counseled on the expected side effects of ciprofloxacin and etoposide, and what to do if/when these occur.

4.4 Management of Toxicity

The National Cancer Institute (NCI) Common Toxicity Criteria for Adverse Events version 4 (CTCAE) will be used to grade toxicity (<http://ctepinfo.nih.gov/>). In Cycle 1 of Phase Ib, any patients developing DLT will be permanently withdrawn from the study.

In Phase Ib and in Phase II, for subjects receiving Cycle 2 or beyond, any toxicity which delays treatment beyond day 42 of a cycle will result in permanent withdrawal of the subject from the study. In addition, toxicity which results in missing more than ½ of all doses of etoposide or ciprofloxacin will result in permanent withdrawal from the study.

The following applies to toxicity occurring in Phase Ib or Phase II except as stated:

4.4.1 Non- Hematologic Toxicity

For any Grade 3 or greater non-hematologic adverse event (AE), deemed related or possibly related to the study intervention and/or the discretion of the investigator, the subject to stop the study drugs.

Management of non-hematologic toxicities such as nausea, vomiting, mucositis, enteritis, and/or diarrhea will follow institutional guidelines.

4.4.1.1 Infection

For any severe infection, study treatment will be held until the infection is controlled. If the infection occurs during the treatment period, missed doses will not be made up.

Management of infection will follow standard institutional guidelines.

4.4.1.2 QTc Interval

Asymptomatic prolonged QTc has been reported with quinolones, although it is not very common with ciprofloxacin. If borderline increases (0.43 to 0.45 sec in men, 0.45 to 0.47 sec in

women) in QTc are noted during screening and before each new cycle, the following are recommended:

- Maintain serum potassium > 4.0 mmol/L and serum magnesium > 2.0 mg/dL whenever possible; and
- Medications with the potential for QTc prolongation should be avoided when possible while on ciprofloxacin.

12-lead ECG recordings will be obtained during screening, on Cycle 1 Day 8, Cycle 1 Day 28, and when clinically indicated.

CTCAE V4 Grade 3 toxicity criteria for the QTc interval is ≥ 501 msec on at least two separate ECGs (Fredericia correction). If this occurs, the subject will be placed on a cardiac monitor and cardiology consultation will be obtained for confirmation. If confirmed, potassium and magnesium supplementation will be given as above. For subjects in Cycle 1 of Phase Ib, this event represents a DLT and the subject will be permanently removed from the study. For subjects beyond Cycle 1 of Phase Ib and for those in Phase II, therapy will be held until eligibility criteria are met.

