Safety Assessments:	
Subjects will be evaluated weekly during and for at least 28 days following the last cycle of chemotherapy. Assessments will include (See Table 1):
 
 • Interval history, review of systems, medications, new allergies, and physical examination with vital sign measurements; • Weekly laboratory assessments, including a CBC with differential and CMP; and • Toxicity assessment per the NIH Common Toxicity Criteria Adverse Event (CTCAE) version 4.
Efficacy Assessments:	
Efficacy parameters used to assess response include hemoglobin, ANC, platelet count, circulating blasts, and bone marrow aspirate and/or biopsy.

Sample Size Estimation	
In prior clinical trials of oral etoposide in resistant AML the CR rate has been approximately 20%. It is expect that the combination of etoposide with ciprofloxacin will improve CR to 40%. In order to detect this difference with type I error rate of 0.10 and power of 80%, when the true response rate is 40%, a minimum of 24 evaluable subjects will be treated in Phase II based on the Simon’s two-stage MiniMax design. Accounting for 15-20% drop out rate, a total of 30 subjects will need to be recruited to this phase.

Table 1. Study Events Schedule

Assessment	Screen (≤ 21 days prior to Day 1)	Cycle 1					Cycle 2		End of Treat- ment ¹² ± 7days	Long- Term Follow Up ¹³
		Day 1	Day 8±2	Day 15±2	Day 22±2	Day 28±2	Days 1, 8, 15, 22±2	Day 28±2		
Signed Informed Consent	X									
Demographics	X									
Medical /Treatment History	X									
Medication History ¹	X	X	X	X	X	X	X	X	X	
Interval History/Physical Examination	X	X	X	X	X	X	X	X	X	
Toxicity Assessment		X	X	X	X	X	X	X	X	
Review of Systems		X	X	X	X	X	X	X	X	
Weight	X	X	X	X	X	X	X	X	X	
ECOG Performance Status	X	X	X	X	X	X	X	X	X	
12-lead electrocardiogram (ECG) ²	X		X			X			X	
Vital Signs ³	X	X	X	X	X	X	X	X	X	
Hematology Laboratory Evaluations ⁴	X	X	X	X	X	X	X	X	X	
Blood Chemistry Laboratory Evaluations ⁵	X	X	X	X	X	X	X	X	X	
Serum Pregnancy Test (females) ⁶	X					X		X	X	
Administer Ciprofloxacin ⁷		X	X				X			
Administer Etoposide ⁸			X				X			
Bone Marrow Aspirate and/or Biopsy ⁹	X					X		X	X	
Adverse Events Assessments ¹¹	X	X	X	X	X	X ¹³	X	X	X	
Survival Assessment										X

¹ Document all medications taken during the two (2) weeks prior to screening and throughout and for 28 days after last treatment.

² Includes: rhythm, rate, and PR, QRS, and QTc intervals.

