3.2.2 Ciprofloxacin

Ciprofloxacin is a quinolone antibiotic which works by inhibiting DNA gyrase (17, 18). Ciprofloxacin is a Topo II inhibitor and in-vitro and xenograft tumor models have shown that this drug has anti-proliferative and possibly pro-apoptotic activity (19-23) at concentrations ranging from 12-800 mcg/ML (19, 20, 23-27). The use of ciprofloxacin in the current trial is based on the ability of this drug to inhibit Metnase and thereby enhance the activity of etoposide in subjects with resistant acute leukemia. Hromas et al demonstrated that ciprofloxacin potentiated the activity of etoposide on AML cell lines at a concentration of 2 µmol/L (0.662µg/mL based on its molecular weight of 331) (4).

Per the prescribing information, a single dose of 250 mg, 500 mg, 750 mg, and 1000 mg of oral ciprofloxacin in healthy volunteers achieved a C_{max} of 1.2, 2.4, 4.3 and 5.4 µg/mL (28). The elimination half-life of ciprofloxacin is 4 hours, and PK studies have shown the mean serum concentrations at 12 hours after a single dose of 250 mg, 500 mg, and 750 mg were 0.1, 0.2 and 0.4 µg/mL, respectively.

The 750 mg twice daily as a starting dose was chosen because this dose results in sustained levels that approximate those shown to augment etoposide effect ([See Table 2](#)) (4). Further, this dose is commonly used for treatment of infection and has been well tolerated (28). To achieve a steady state concentration prior to initiation of etoposide, ciprofloxacin will be started 24 hours before etoposide is begun. If the starting dose of ciprofloxacin is tolerated, a higher dose of 1,000 mg twice daily will be explored in order to further increase ciprofloxacin 12 hour levels. Although less commonly used, this dose has also been well tolerated in studies in normal volunteers and in subjects with infection (29, 30).

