4.1 Etoposide and Ciprofloxacin

Ciprofloxacin will be administered orally twice daily on Days 1 to 10 of each 28-day cycle. Whenever possible, doses should be taken at 0800 hours and 2000 hours. If for some reason the doses are not taken at these times, ciprofloxacin can be taken as late as 6 hours after the scheduled time. If > 6 hours elapses, that dose of ciprofloxacin will be held and not made up. The starting dose will be 750 mg (dose level 0) with escalation to a maximum of 1000 mg (dose level +1) or de-escalation to a minimum of 500 mg (dose level -1).

Etoposide at a fixed dose of 200 mg will be administered orally once daily on Days 2 to 8 of each 28-day cycle. Subjects will be instructed to take etoposide with their morning dose of ciprofloxacin at 0800 hours on an empty stomach. If for some reason the dose is not taken at this time, it may be taken as late as 6 hours after the scheduled time. If >6 hours elapses, that dose of etoposide will be held and not made up.

A medication diary will be given to all subjects and they will be instructed to record the actual times they take both etoposide and ciprofloxacin. Doses missed will be recorded as such. Subjects will be told to call within 12 hours of missing a dose. Subjects will be instructed to bring the diary and any unused medication with them to all study visits. Any unused medication will be disposed of per institutional standard practice.

Subjects in Cycle 1 of Phase Ib who miss any etoposide or ciprofloxacin doses will be considered evaluable only if a DLT occurs. Otherwise they will be removed from the study on Day 28 and replaced in the cohort in which they were treated. Subjects in Phase Ib beyond the first cycle and those in Phase II will be considered evaluable for response if they have received at least one cycle in accord with the protocol. For these subjects non-compliance with dosing will be dealt with at the discretion of the PI.

Standard administration instructions will be given to each subject for ciprofloxacin (*e.g.*, separating administration from dairy products, calcium-fortified juices, sucralfate, antacids, or other medications that contain aluminum, magnesium, calcium, iron, or zinc). Subjects will be advised not to consume grapefruit or grapefruit juice within 7 days prior to starting ciprofloxacin and until 7 days after completion of all doses of ciprofloxacin on study.

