 - BUN, creatinine, uric acid, total bilirubin, AST, ALT, alkaline phosphatase, LDH, sodium, potassium, calcium, magnesium, phosphorous, bicarbonate, chloride, glucose, albumin, and total protein.

Cycle 1 Day 28

The C1D28 visit may occur \pm 48 hours from the protocol-specified date. All subjects will have the following procedures:

- Document concomitant medications and transfusions;
- AE assessment;
- Physical exam;
- Vital signs, including blood pressure, pulse, respirations, and temperature;
- Weight;
- 12-lead electrocardiogram (ECG), including rhythm, heart rate, and PR, QRS, and QTc intervals;
- ECOG Performance Score;
- Hematology laboratory evaluations:
 - Complete blood count (CBC) including hemoglobin, hematocrit, white blood cell (WBC) absolute differential including circulating blasts, and platelet count;
- Blood chemistry laboratory evaluations:
 - BUN, creatinine, uric acid, total bilirubin, AST, ALT, alkaline phosphatase, LDH, sodium, potassium, calcium, magnesium, phosphorous, bicarbonate, chloride, glucose, albumin, and total protein;
- Bone marrow aspirate and/or biopsy for clinical classification (cellularity, blast assessment) and cytogenetic testing, ; and
- Serum or urine pregnancy test – if applicable for females of childbearing potential.

At C1 D28, the subject will have completed protocol-specified treatment for Cycle 1. For subjects in Phase Ib, DLT assessment will occur at this point.

Cycle 2/Days 1, 8, 15, and 22

All subjects will have the following procedures completed on the visit, unless otherwise specified:

- Document concomitant medications and transfusions;
- AE assessment;
- Physical exam;
- Vital signs, including blood pressure, pulse, respirations, and temperature;
- Weight;
- ECOG Performance Score;
- Hematology laboratory evaluations (unless performed in the 24 hours prior to visit):
 - Complete blood count (CBC) including hemoglobin, hematocrit, white blood cell (WBC) absolute differential including circulating blasts, and platelet count; and

- Blood chemistry laboratory evaluations (unless performed in the 24 hours prior to visit):
 - BUN, creatinine, uric acid, total bilirubin, AST, ALT, alkaline phosphatase, LDH, sodium, potassium, calcium, magnesium, phosphorous, bicarbonate, chloride, glucose, albumin, and total protein.

Cycle 2 /Day 28 (± 2) and EOT (± 7)

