The Day 28 visit may occur ± 48 hours and EOT may occur within 7 days from the protocol-specified date. All subjects will have the following procedures:

- Document concomitant medications and transfusions;
- AE assessment;
- Physical exam;
- Vital signs, including blood pressure, pulse, respirations, and temperature;
- Weight;
- ECOG Performance Score;
- Hematology laboratory evaluations:
 - Complete blood count (CBC) including hemoglobin, hematocrit, white blood cell (WBC) absolute differential including circulating blasts, and platelet count;
- Blood chemistry laboratory evaluations:
 - BUN, creatinine, uric acid, total bilirubin, AST, ALT, alkaline phosphatase, LDH, sodium, potassium, calcium, magnesium, phosphorous, bicarbonate, chloride, glucose, albumin, and total protein;
- Bone marrow aspirate and/or biopsy for clinical classification (cellularity, blast assessment) and cytogenetic testing; and
- Serum or urine pregnancy test – if applicable for females of childbearing potential
- 12-lead electrocardiogram (ECG), including rhythm, heart rate, and PR, QRS, and QTc intervals (only at EOT)

If a subject achieves CR, or at end of treatment bone marrow assessments will be performed as clinically indicated.

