7.2.5 Physical Examination, Vital Signs and ECG

A physical examination and vital signs (systolic and diastolic blood pressure, pulse rate, respiratory rate, and temperature) will be conducted during the Screening period and on each study visit (Days 1, 8, 15, 22, and 28) of every cycle of CE. A 12-lead ECG (rhythm, heart rate, and PR, QRS, and QTc intervals) will be performed during the Screening period, on Cycle 1 Day 8, Cycle 1 Day 28, and as clinically indicated.

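### No ECG is scheduled on the ten ciprofloxacin days of Cycle 2, so in that cycle the QTc hold rule depends on ECGs ordered on clinical indication

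*Combined protocol and SAP*

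**What the plan says.** **Exposure.** Section 4.1: "Ciprofloxacin will be administered orally twice daily on Days 1 to 10 of each 28-day cycle". Section 3.2.2: "The elimination half-life of ciprofloxacin is 4 hours".

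**QTc as a named risk.** A prolonged baseline QTc is an exclusion criterion. QTc prolongation of Grade 3 or worse is a dose-limiting toxicity (section 3.3.2, item 5). Section 4.4.1.2 is devoted to its management. There, Grade 3 means 501 msec or more on at least two separate ECGs. In Cycle 1 of Phase Ib this is a DLT and the subject leaves the study. Otherwise: "For subjects beyond Cycle 1 of Phase Ib and for those in Phase II, therapy will be held until eligibility criteria are met".

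**ECG schedule.**
- Section 4.4.1.2: "12-lead ECG recordings will be obtained during screening, on Cycle 1 Day 8, Cycle 1 Day 28, and when clinically indicated".
- Section 7.2.5: screening, then "on Cycle 1 Day 8, Cycle 1 Day 28, and as clinically indicated".
- Table 1: screening, Cycle 1 Day 8, Cycle 1 Day 28 and End of Treatment. The two Cycle 2 columns are blank.
- Section 6.2: the list headed "Cycle 2/Days 1, 8, 15, and 22" has no ECG. The combined Cycle 2 Day 28 and end-of-treatment list has "12-lead electrocardiogram (ECG), including rhythm, heart rate, and PR, QRS, and QTc intervals (only at EOT").

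**The concern.** The plan asks for action on a QTc finding in Cycle 2, but no scheduled measurement in that cycle is taken while the drug is present. A subject with a normal reading on Cycle 1 Day 8 whose QTc lengthens in Cycle 2, for instance after a change in co-medication, could pass through the whole schedule without an on-drug ECG. Section 5.2 leaves room for such a change. Subjects on Appendix C drugs may take part if they meet the QTc criteria, and most prophylactic antimicrobials are left to the treating physician.

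Two things are at stake. The hold rule may not be applied when it should be. And the scheduled Cycle 2 QTc data of completers are washout values, which cannot show an on-drug effect. ECGs are a listed safety variable (section 7.1.1), and safety is a secondary objective (section 2.2).

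**Working it through.** The plan states no figure for this interval, so the check is schedule arithmetic.

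**Inputs.** Last ciprofloxacin day: Day 10 of each cycle (section 4.1). Half-life: 4 hours (section 3.2.2). Windows: ±2 days for Day 8 and Day 28, ±7 days for end of treatment (Table 1, section 6.2). Assumptions: all ten days of ciprofloxacin are taken, and a completer's end-of-treatment visit is centred on Cycle 2 Day 28, as the joint heading in section 6.2 suggests.

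**Step 1: distance from dosing.** Days after last dose = ECG day − 10. Half-lives = days × 24 / 4 = days × 6.

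| Scheduled ECG | Window | Days after last dose (early / nominal / late) | On drug? |
|---|---|---|---|
| Screening | before Day 1 | not applicable | No |
| Cycle 1 Day 8 | Days 6-10 | −4 / −2 / 0 | Yes |
| Cycle 1 Day 28 | Days 26-30 | 16 / 18 / 20 | No |
| End of treatment after a full Cycle 2 | Days 21-35 | 11 / 18 / 25 | No |

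Nominally, 18 × 6 = 108 half-lives. At the early edge of the end-of-treatment window, 11 × 6 = 66.

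**Step 2: Cycle 2 coverage.** Of the Cycle 2 visits (Days 1, 8, 15, 22, 28), Days 1 and 8 fall within Days 1-10. Neither has an ECG in Table 1 or section 6.2. Scheduled on-drug ECGs in Cycle 2: 0 over 10 dosing days. A two-cycle subject has 2 × 10 = 20 ciprofloxacin days and 4 scheduled ECGs, of which 1 is on drug.

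**Step 3: what each ECG can set in motion.**
- Cycle 1 Day 8: in Phase Ib it feeds the DLT branch. In Phase II it can start the hold rule, while ciprofloxacin is still being taken at the nominal day.
- Cycle 1 Day 28: an off-drug check before Cycle 2. In Phase II an abnormal result could delay Cycle 2, but it says nothing about what happens under Cycle 2 dosing.
- End of treatment, completer: no study therapy remains to be held.
- End of treatment, early withdrawal: section 6.3 places this visit at withdrawal, so it may fall near or during the dosing days, but treatment has already stopped.

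The Grade 3 criterion needs two separate ECGs, so a scheduled ECG would open the process rather than complete it. In Cycle 2 there is no scheduled first ECG during dosing.

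**Step 4: agreement between places.** All four places agree that nothing is scheduled on Cycle 2 Days 1-10. They differ on the end-of-treatment ECG: Table 1 and section 6.2 include it, and sections 4.4.1.2 and 7.2.5 omit it. Section 6.3 sends completers to section 7.2 for their end-of-treatment assessment, and section 7.2 is where the ECG is missing.

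**The case against.** The other side has real points.

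- **Other controls exist.** Section 5.2 makes QTc-prolonging drugs relatively contraindicated on Days 1-12 of each cycle, restricts fluconazole and discourages voriconazole, and asks for a medication review at each visit. Section 6.2 schedules potassium, magnesium and calcium at the Cycle 2 visits. Any of these could prompt an ECG, since clinical indication is not limited to symptoms. This stands as mitigation. These controls address risk factors, however, and do not measure QTc.
- **The risk may be small.** Section 4.4.1.2 calls prolongation not very common with ciprofloxacin. There is no dose escalation within a subject, and 108 half-lives leave no carry-over into Cycle 2. This limits the weight of the point. It does not cover co-medication or electrolytes that change between cycles.
- **A Day 8 ECG comes late.** At Day 8, 10 − 8 = 2 ciprofloxacin days remain (4 at Day 6, none at Day 10), and Day 8 is the last etoposide day. This is true, and equally true of the Cycle 1 Day 8 ECG the plan already relies on.

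A reader might infer more than the documents support:
- That the hold rule has no scheduled trigger at all. It also covers Phase II Cycle 1, where the Day 8 ECG can trigger it.
- That ECGs on clinical indication will not happen. They may not; the controls above could lead to them.
- That the trial understates QTc toxicity by some amount. No incidence is given, section 11.3.1 plans only listings of ECG data by visit, and the on-drug Cycle 1 Day 8 readings remain in the dataset.
- That the passages contradict each other on Cycle 2 dosing. They agree in scheduling nothing there.

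**Conclusion.** The gap is real and confined to Cycle 2. For subjects treated in Cycle 2 there are no scheduled on-drug ECGs over ten dosing days. For completers, the one scheduled ECG after Cycle 2 starts is nominally 18 days after the last dose (11-25 with the window). In that cycle the hold rule depends on unscheduled ECGs, and the scheduled QTc data of completers cannot show an on-drug effect.

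This rests on Days 1-10 being dosed in full and on end of treatment being centred on Cycle 2 Day 28. The conclusion is not sensitive to the second assumption, because even the earliest visit in the window is 66 half-lives after dosing. How often a prolongation would be missed cannot be estimated from the documents. The point is a worthwhile low-cost correction to safety monitoring; it does not affect the response-rate analysis.

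**What to change.** Reconcile the ECG schedule with the QTc rule in section 4.4.1.2, so that Cycle 2 has a scheduled ECG at an existing visit during dosing. The Cycle 2 Day 8 visit already exists and mirrors Cycle 1 Day 8. For Cycle 2 completers it could take the place of the post-washout end-of-treatment ECG. Keep the end-of-treatment ECG for subjects who withdraw early, and keep Cycle 1 Day 28 as the check before Cycle 2. The sponsor may settle on another time within dosing.

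Make Table 1 and section 6.2 agree with sections 4.4.1.2 and 7.2.5 on the end-of-treatment ECG, and correct the cross-reference in section 6.3 to match.

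The cost is a protocol amendment. A completer still has four scheduled ECGs and no added visit. The downside is that completers lose their routine post-treatment ECG unless one is clinically indicated. No change to any dose, QTc threshold or hold rule is proposed.
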